Primary Objective	To determine if standard of care radiation exposure longitudinally effects the accuracy and precision of the G6 transmitter in the post TPIAT inpatient population
Secondary Objective(s)	Reduce burden for patients to remove and waste a functional and expensive Dexcom G6 CGM for radiologic procedures.
Research Intervention	Participants will have their study provided Dexcom G6 CGM uncovered for standard of care procedures that involve radiation exposure while inpatient at CCHMC
IND/IDE #	NA
Study Population	Post total pancreatectomy with islet autotransplantation (TPIAT) patients
Sample Size	N = 40
Study Duration for individual participants	3 months of active study participation

Abbreviations	total pancreatectomy with islet autotransplantation (TPIAT) Identification, ID Principal Investigator, PI Good Clinical Practice, GCP Adverse Reactions, AE Severe Adverse Reactions, SAEs continuous glucose monitoring (CGM) point of care (POC) Data and Safety Monitoring Board (DSMB) Standard of Care (SOC)
----------------------	--

Study Objective

We will establish accuracy and precision data for the lifespan (up to about 3 months) of the Dexcom G6 transmitter exposed to inpatient radiation (x-ray and/or CT scan) that is not covered with lead apron.

Background

There are limited data published regarding the accuracy and precision of continuous glucose monitoring (CGM) devices after radiation exposure. While manufacturers, specifically Dexcom, recommend to remove CGM systems with MRI and CT scan there is some ambiguity surrounding radiation exposure from a diagnostic x-ray as only a few cross-sectional studies have been conducted [1]. Spanakis et al assessed the accuracy and precision of Dexcom two hours pre- and post-imaging. They reported that ongoing CGM use during multiple radiology procedures was safe and reliable based on 98.1% of glucoses falling into Zone A and B of Clark Error Grid analysis which represents values that result in no difference in clinical decision making. However, this analysis did not assess the transmitter longitudinally to ensure accuracy over its 3-month lifespan. A second report, based on simulation of a radiotherapeutic procedure (80 GY) found that the components of G6 retained basic functionality and data integrity after exposure and again did not include assessment of the transmitters 3-month lifespan.

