Hydroxyurea a known substance to interfere with CGM sensor values is started approximately day 7 post-TPIAT and can result in erroneously elevated glucose sensor value 6-9 hours post-administration [2]. For this reason, data from 10 hours post Hydroxyurea dosing will not be used in the initial data analysis.

Study Intervention:

Enrolled participants will NOT have a lead apron used to cover their Dexcom G6 transmitter during radiation exposure procedures performed while participant is inpatient post TPIAT.

Transmitter accuracy and precision will be monitored for 3 months post TPIAT or until the transmitter is changed.

Study Procedures:

Our main goal is to assess the accuracy and precision of the Dexcom G6 transmitter readings after radiation exposing SOC procedures for which the transmitter is uncovered compared to publicly available accuracy data. Transmitter function will be assessed by comparing the device readings to glucometer readings.

Patients undergoing a TPIAT and planned to receive a Dexcom G6 CGM will be approached for participation in this study prior to post surgery CGM placement.

An anticipated 40 participants will be enrolled and will NOT have a lead apron used to cover their Dexcom G6 device during radiation exposure procedures performed while participant is inpatient post TPIAT.

Dexcom G6 CGM data and point of care (POC) testing with a glucometer (such as the ACCU-CHEK® Inform II Meter) will be utilized for this study while inpatient and a standard issue meter when outpatient. While participants are inpatient POC monitoring will occur every 1 hour when insulin administration is administered intravenous and every 3 hours with the transition to subcutaneous insulin administration. Inpatient POC glucose values and Dexcom reports will be collected. Once discharged, CGM and glucometer readings will be collected by downloading readings using software at the 1 (+/-3 days) week post discharge clinic visit, 1 month (+/- 7 days) post TPIAT, 2 months (+/- 7 days) post TPIAT and before the transmitter is due to be changed (expected 3 months (+/- 7 days) post TPIAT).

The Dexcom CGM has an online platform called Clarity that can generate reports or raw data files of continuous glucose readings. The home glucometer used for the study has a mobile app that can generate reports or raw data files of glucometer readings. Reports will be reviewed at the time of set data download time points by delegated study staff.

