Downloaded data will be stored on a secure server utilizing the participants study ID.

Participants will be requested to check their glucose values with the Contour glucometer 4 times a day for the ten days leading up to study data requests at study time points, but we will accept a minimum of 2 times per day the 7 days prior to a scheduled download to compare the functionality of the Dexcom G6 CGM. Participants (or parents) will be contacted and reminded to check blood sugars at the beginning of this 10-day period at each time point.

While participant is inpatient post TPIAT and outpatient for the life of the CGM transmitter, the number of and type of radiation procedure will be collected from their EMR.

After discharge participants will be contacted at the 1 (+/-3 days) week post discharge clinic visit, 1 month (+/- 7 days) post TPIAT, 2 months (+/- 7 days) post TPIAT and before the transmitter is due to be changed (expected 3 months post TPIAT). Participants will be asked to provide information on any radiation procedures that may have occurred outside of CCHMC, and study staff will confirm the transmitter has not yet been changed. If at any point the transmitter is changed for any reason, the participant will no longer be actively enrolled in the study but data for the transmitter will be collected. If the transmitter is changed due to clinical recommendations such as due to technical issues with readings or calibrations or due to radiologic procedures in which it is in the field of interest, they will be considered completed in the study. If the transmitter is changed due to participant preference with no reason to believe the transmitter was not working properly or needed to be removed for clinical procedures then the participant will be withdrawn. Any termination of participation prior to the anticipated approximately 3-month post TPIAT time point will be noted with reason for early completion/withdraw recorded.

Formal statistical analysis will assess accuracy of the Dexcom transmitter between the publicly available accuracy data and the enrolled participant data. Performance evaluation will include the proportion of CGM values within +/-20% of the reference (POC) glucose values > 100 mg/dL or within +/-20 mg/dL of reference glucose values < 100 mg/dL (%20/20, the analogous %15/15, and the mean absolute relative difference (MARD, expressed as a percentage)

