CONTROL GROUP: Publicly available accuracy data from Dexcom

EXPOSURE GROUP: patients who will NOT have the CGM covered during radiologic procedures involving x-rays.

Standard of care at CCHMC is that sensor values do not replace point of care (POC) testing with a glucometer (such as the ACCU-CHEK® Inform II Meter) while inpatient. POC monitoring will occur every 1 hour when insulin administration is administered intravenous and every 3 hours with the transition to subcutaneous insulin administration. After discharge a provider and family may choose to space out these glucometer readings and eventually transition to relying only on CGM values for SOC, but for this study we are asking families to conduct regular glucometer checks to have comparison data at our study time points.

The following data will be collected during the life of the transmitter (approximately 3 months after placement):

- POC glucose values (from inpatient and outpatient glucometers)
- Dexcom CGM Clarity reports (inpatient and outpatient)
- Timing of interfering substances (hydroxyurea)
- Dates of clinically indicated x-rays and CT scans and radiation exposures (RADS) to radiation field of interest
- Indication for radiologic testing (nausea, vomiting, fever, pain, etc)
- Documentation of apron use during radiologic assessment

The G6 transmitter will be issued while inpatient and be sent home with the families at discharge. Assessment of Dexcom reports compared to POC and home monitoring will be collected at 1 (+/-3 days) week post discharge clinic visit, 1 month (+/- 7 days) post TPIAT, 2 months (+/- 7 days) post TPIAT and before the transmitter is due to be changed (expected 3 months post TPIAT).

Two endocrine providers will perform the clinical assessment of the outpatient reports of glucometer and CGM. Formal analysis will be completed after 3 months of transmitter data is collected.

Statistical Consideration

Several accuracy methods will be ascertained. The %20/20 and%15/15 will be assessed from the participant's medical record for both inpatient and outpatient settings will be reviewed. In addition, use of Clark Error Grid Analysis will be performed on data points collected after 10 hours of hydroxyurea dosing.

Recruitment

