Participants will be provided a study Dexcom G6 transmitter and initial sensor, and any additional needed sensors during the 3-month participation period per participant. The information gained from this study outweighs any perceived risk as it may provide documentation that after minimal radiation exposure the accuracy of the sensor and transmitter is unaffected. Subsequently, it would no longer be necessary to remove device and waste expensive supplies with radiologic studies. These benefits would apply to all Dexcom G6 wearers.

To aid study data consistency, participants who are not using a glucometer approved by the study will also be provided this device and needed supplies for the 3-month study window.

Data Management and Confidentiality

Participants will be assigned a participant ID, which will be used to associate participants to participant data and CGM results. Participant identification will be kept in the form of an enrollment log. The enrollment log will be destroyed at the earliest opportunity.

Dexcom CGM and POC glucometer data will be saved on a secure server in the form of study participant ID labeled Excel files. The study will also collect demographic information (such as age, gender, BMI), radiologic studies performed (type and procedure data) and date of operation and date of discharge. Study data will be stored on a secure sever.

Collected data will be kept confidential and will only be shared with authorized study staff.

Provisions to Monitor the Data to Ensure the Safety of Subjects.

Adverse event monitoring: No surgery related complications will be tracked for this study, only events relating to the function of the study CGM will be collected.

Monitoring and auditing procedures will be followed to ensure that the study is conducted, documented, and reported in accordance with the IRB approved protocol, the International Conference on Harmonization (ICH) Good Clinical Practice (GCP) Guidelines, and applicable regulatory requirements of Cincinnati Children's Hospital Medical Center.

An independent medical monitor will assess the progress of this clinical study, the safety data, critical efficacy endpoints and provide recommendations to study personnel annually.

Provisions to Protect the Privacy Interests of Subjects

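### The protocol hopes to document that accuracy is unaffected, but the open comparison with public data has no margin, confidence-limit rule or lead measure by which that could be concluded

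*Combined protocol and SAP*

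**What the plan says.** The primary objective in the Study Summary is neutral: "To determine if standard of care radiation exposure longitudinally effects the accuracy and precision of the G6 transmitter in the post TPIAT inpatient population". Potential Benefits to Subjects goes further. It says of the study that "it may provide documentation that after minimal radiation exposure the accuracy of the sensor and transmitter is unaffected", and draws a consequence for practice: "Subsequently, it would no longer be necessary to remove device and waste expensive supplies with radiologic studies". The same section extends the benefit to every wearer of the device.

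The analysis meant to carry this is given in Study Procedures: "Formal statistical analysis will assess accuracy of the Dexcom transmitter between the publicly available accuracy data and the enrolled participant data". Analysis and Methods defines the comparator: "CONTROL GROUP: Publicly available accuracy data from Dexcom". No numeric reference value is given.

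On measures, Study Procedures lists %20/20, %15/15 and MARD, beginning "Performance evaluation will include the proportion of CGM values within +/-20% of the reference (POC) glucose values > 100 mg/dL". Statistical Consideration opens with "Several accuracy methods will be ascertained" and adds the error grid. Study End Points adds time to transmitter replacement. On size, "An anticipated 40 participants will be enrolled"; Recruitment and Available Resources support that number by feasibility alone.

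No section gives a hypothesis, test, significance level, confidence interval, margin, performance goal or lead measure.

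**The concern.** To conclude that accuracy is unaffected, the data must rule out a loss large enough to matter, so that loss has to be stated. The 20% and 20 mg/dL limits do not do this. They classify a single reading and say nothing about how much worse the exposed group may be than the reference.

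Without a stated loss, two readings of the same data are open. A real loss could go undetected and be reported as no effect. Conversely, a trivial gap could be reported as an effect if repeated readings from one participant are treated as independent. With four measures, and with inpatient data and four outpatient time points, the most favourable result could also be chosen after the data are seen. At stake is a change in practice: leaving the device on during imaging.

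**Working it through.** **The plan's own figure.** N = 40 cannot be reproduced or refuted, because no significance level, power, SD, effect or margin stands behind it. What follows is illustration.

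**Inputs.** From the documents: n = 40; at each of four outpatient time points, at least 2 × 7 = 14 and as requested 4 × 10 = 40 meter readings. Assumed: between-participant SD of %20/20 of 10 points (range 6 to 12), two-sided 5% level, public value taken as fixed, benchmark 92%, and 28 participants as an example of a reduced evaluable number.

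**Precision.** SE = SD/√n = 10/√40 = 1.58. Half-width = t(0.975, 39) × SE = 2.02 × 1.58 = 3.2 points. For SD 6 and 12 it is 1.9 and 3.8. The low end is not reachable in a single window at the accepted minimum: with 14 readings, binomial noise alone gives an SD of 100 × √(0.92 × 0.08/14) = 7.3 points.

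**Chance that a true 3-point loss is non-significant.** One-sample t test, noncentrality 3/SE:

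| SD | 3/SE | Non-significant, n = 40 |
|---|---|---|
| 6 | 3.16 | 13% |
| 10 | 1.90 | 54% |
| 12 | 1.58 | 66% |

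For scale, a 3-point loss from 92% raises out-of-limit readings from 8% to 11%.

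**Same question on MARD.** Normal approximation, assumed SD 2, 4 or 6 points, n = 40: a 1-point worsening is non-significant 11%, 65% or 82% of the time.

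**Clustering.** The outpatient minimum is 40 × 14 × 4 = 2,240 pairs, and the request is 40 × 40 × 4 = 6,400. For one time point, with an assumed rate of 90%, an ICC of 0.05 to 0.30 and design effect 1 + (m − 1) × ICC:

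| Readings each (m) | Half-width, clustered | Half-width, clustering ignored |
|---|---|---|
| 14 | 3.2 to 5.5 points | 2.5 points |
| 40 | 2.5 to 5.2 points | 1.5 points |

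**What a margin would do.** With no true loss, the probability that the lower 95% limit clears a 5-point margin (noncentrality 5/SE) is:

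| SD | n = 40 | n = 28 |
|---|---|---|
| 10 | 87% | 72% |
| 12 | 73% | 57% |

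Five points is not a recommendation. With SD 10 and n = 40, a true 3-point loss would still pass that margin 23% of the time and a 4-point loss 9%. If 3 points is judged relevant, the margin must be smaller than 3. By symmetry with the 54% above, a 3-point margin is met only 100 − 54 = 46% of the time with no true loss.

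**The case against.** The strongest reply is that the protocol never commits to a no-effect claim. Its primary objective is neutral, its stated aim is to add to the knowledge base, and the hoped-for conclusion appears only under benefits, qualified by may. The analysis sentence does not restrict the comparison to a difference test. An estimate with a confidence interval would fit it and could exclude a relevant loss. Time to replacement and review by two endocrine providers also add information.

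Much of this stands. A reader might infer that the sponsor will treat non-significance as proof of no effect. The documents do not say so, and they name no test or p-value. A reader might also infer that the whole trial is designed to prove no effect; the neutral objective does not support that. A descriptive report with intervals is a legitimate alternative to a margin.

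What does not stand is the sentence under Potential Benefits. It names a conclusion and a change in practice that nothing in the analysis sections defines how to reach. Neither the replacement endpoint nor the clinical review supplies an allowed loss of accuracy.

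**Conclusion.** The gap is real. The benefit claim goes beyond the analysis, and no rule says when the data would support it, so a non-significant or favourable-looking result on any one measure could be read as no effect. That finding rests on the text alone. Its size rests on assumptions: the between-participant SD, the fixed benchmark and complete data on 40 participants. Under these, a 3-point loss in %20/20 escapes detection about half the time, within a wide range of 13% to 66%.

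It is tempting to conclude from this that 40 participants are too few. The figures do not show that: 40 is ample for some pairs of SD and margin and short for others, and the documents give no basis for choosing between them.

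**What to change.** 1. Name one lead measure. An example is %20/20 averaged per participant over all post-exposure check windows, using all readings from the original transmitter up to its replacement. Keep transmitters replaced early for technical problems in this analysis and report them beside time to replacement. The other measures and the 3-month window are supportive. The 3-month window should not lead: Study Procedures counts participants whose transmitter was changed for technical problems as completed, so that window would hold only surviving transmitters and favour a finding of no loss.
2. Before outcome data are viewed, state the public reference value, its source, and a justified margin smaller than any loss considered clinically relevant.
3. Conclude no relevant loss of accuracy only if the participant-level (clustered) 95% confidence limit for study minus reference excludes that margin. Otherwise report that it was not shown, whatever the p-value.

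If the sponsor will not commit to a margin, report participant-level estimates with confidence intervals, call the study descriptive, and remove from Potential Benefits to Subjects the statements that accuracy is unaffected and that removal is no longer needed.

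Cost: the change is to wording and analysis and needs no new data collection. The claim becomes harder to make, as the pass probabilities above show, and a tight margin may not be attainable with 40 participants. A margin also does not remove confounding from the external comparator, so a gap, or its absence, still could not be attributed to radiation on this basis alone.

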At CCHMC, we are in the unique position to work with a hospitalized population who utilize Dexcom G6 CGMs while inpatient. The patients are children and adolescents who have had a total pancreatectomy with islet autotransplantation (TPIAT) and receive, on average, 6 radiology procedures (defined as CT scans or x-rays) over a 2-week period following TPIAT. This population has a target glucose range of 80-120 mg/dL and Dexcom is used to monitor trends under careful oversight by the pediatric endocrinology service. Because these patients represent a complex surgical population, they often have post-operative events that include abdominal pain, vomiting, and fever. Radiology procedures are frequently obtained for

assessment of obstruction, abscesses and/or thrombi. At our institution if the sensor and transmitter is not in the field of interest, current practice is to cover the Dexcom (sensor and transmitter) during all radiology procedures with a lead apron and have careful assessment of sensor values compared to glucometer glucose readings while in-hospital and the 3 months post-operatively. The repeated radiation exposure over a short timeframe (2-3 weeks) in the context of established monitoring of device performance by providers who specialize in pediatric diabetes management makes this population ideal for studying CGM performance. A transmitter is changed every 3 months and a sensor is changed every 7-10 days.

Rationale

It is of great burden for patients to remove and waste functional and expensive medical equipment for radiologic procedures, especially if there are repeated procedures planned over a short period. There is minimal data to suggest, at least in the short term, that accuracy and precision is not affected by radiation in commonly ordered radiology procedures. Our aim is to contribute to this knowledge base and assess *longitudinally* the accuracy and precision of the G6 transmitter during and after exposure to radiation in an inpatient post-TPIAT population.

Study End Points:

CGM readings will be assessed for accuracy and precision. Publicly available accuracy data will be compared to study glucometer readings over the 3 months expected lifespan of the Dexcom G6 CGM transmitter used post TPIAT.

Time to Dexcom G6 CGM transmitter replacement needed over the 3 months post TPIAT will be compared to the standard device life expectancy.

We will take the following into consideration with our analysis:

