between temporally matched CGM and reference values (Wadwa et al. Diabetes technology & Therapeutics. 20:6 2018).

Data and Specimen Banking

De-identified data will be retained for future potential research or FDA submission. No specimens will be collected for this study.

Sharing of Results with Participants

Study participants will be informed immediately if the Dexcom G6 CGM that they are utilizing is malfunctioning. Additionally, after final analysis participants will be informed of the result of the study by a study team member. This information will be communicated to the participants verbally or by written communication based on participant's preference.

Study Timelines

The study will commence after Dexcom Company and local IRB approval. In addition, support of a study coordinator will be required to assist with IRB submission, obtaining consent and insuring protocol procedures both inpatient and outpatient. Proposed start winter 2021. CCHMC performs 1-2 TPIATs per month thus patient recruitment would occur over a 15-19 month period.

Inclusion and exclusion criteria:

Inclusion Criteria: planned TPIAT at CCHMC, staying inpatient at CCHMC post TPIAT, planned to receive a Dexcom G6 CGM.

Exclusion criteria: hemo- or peritoneal dialysis.

Vulnerable populations:

Individuals who are not yet adults will be permitted to participate in the study following written informed consent and assent (if aged 11-17) with said individual and their parent/guardian.

Legal guardians unable to provide consent for their child to participate in the study will not be enrolled.

This study will involve participants that are children and potentially participants that are mentally impaired. To ensure that their rights and welfare are protected we will:

- Make adequate provisions for soliciting assent from children 11-17 years of age
- Make adequate provisions for soliciting parental permission for children and mentally impaired adults.

The risk to participate in the intervention portion of this study holds the prospect of direct benefit for the subject.

Analysis and Methods

This is a prospective assessment of accuracy and precision of the Dexcom G6 after radiation exposure.

All post-TPIAT patients at Cincinnati Children's Hospital Medical Center wear the Dexcom G6 as standard of care and are under the careful surveillance of pediatric endocrinology.

Participants will be enrolled and assigned into the exposure group.

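### No rule separates readings taken before the first uncovered procedure, so unexposed pairs count as exposed and dilute any radiation effect, mainly in the inpatient and pooled estimates

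*Combined protocol and SAP*

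**What the plan says.** Analysis and Methods makes group membership unconditional: "Participants will be enrolled and assigned into the exposure group". It defines the group by the intention to leave the device uncovered, not by a procedure having taken place: "EXPOSURE GROUP: patients who will NOT have the CGM covered during radiologic procedures involving x-rays".

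The entry criteria require no imaging: "planned TPIAT at CCHMC, staying inpatient at CCHMC post TPIAT, planned to receive a Dexcom G6 CGM". Under Study Procedures, patients "will be approached for participation in this study prior to post surgery CGM placement", so enrolment precedes any exposure of the study transmitter. Collection starts at placement: "The following data will be collected during the life of the transmitter (approximately 3 months after placement"). The comparison is stated in Study Procedures: "Formal statistical analysis will assess accuracy of the Dexcom transmitter between the publicly available accuracy data and the enrolled participant data".

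The only stated exclusion of readings is the 10-hour window after hydroxyurea (Study End Points; repeated for the error grid in Statistical Consideration). Procedure dates, number, type and apron use are collected, but no analysis use of them is given. Risk Assessment adds that a device lying in the field of interest is removed, so having a procedure does not by itself mean that the device was exposed.

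**The concern.** A transmitter that has not yet been through an uncovered procedure is unexposed. If its readings enter the exposed accuracy estimate, the radiation component of that estimate shrinks in proportion to their share.

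The share need not be trivial, because reference testing is densest early in the stay: "POC monitoring will occur every 1 hour when insulin administration is administered intravenous", then every 3 hours, and only 2 to 4 checks a day during the outpatient windows.

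Dilution of a radiation effect favours the conclusion that the study hopes to document, namely that accuracy is unaffected (Potential Benefits to Subjects), so it is not conservative. Version 2 also removed the concurrent standard-of-care arm. Inpatient readings before the first exposure are now the main unexposed data from the same patients and the same inpatient meter, and the plan does not set them apart.

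**Working it through.** The plan's N = 40 comes with no alpha, power, effect size or SD, so there is no sample-size figure to reproduce. The check is how many pairs could be unexposed.

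**Inputs from the documents**
- Background: patients "receive, on average, 6 radiology procedures" over 2 weeks. No distribution or time to first procedure is given.
- Inpatient reference tests: 24 a day if hourly, 8 a day if 3-hourly.
- Outpatient reference tests at four time points: minimum 2 × 7 × 4 = 56; requested 4 × 10 × 4 = 160 (windows assumed not to overlap).

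**Assumptions**
- CGM placed at day 0; 14-day stay; 6 procedures uniformly timed over it, all with the device worn and uncovered.
- One CGM pair per reference test, all pairs weighted equally.

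**Time to first procedure.** The expected minimum of 6 uniform times on 14 days is 14/(6+1) = 2 days.

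**Share of unexposed pairs, first procedure at day 2**

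| Inpatient testing | Before first procedure | All inpatient | Share of inpatient | Share of total, 56 outpatient | Share of total, 160 outpatient |
|---|---|---|---|---|---|
| Hourly throughout | 48 | 336 | 14% | 48/392 = 12% | 48/496 = 10% |
| Hourly to day 2, then 3-hourly | 48 | 48 + 96 = 144 | 33% | 48/200 = 24% | 48/304 = 16% |
| 3-hourly throughout | 16 | 112 | 14% | 16/168 = 10% | 16/272 = 6% |

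The range for all pairs is therefore about 6-24%. The top figure is for a participant whose first procedure falls exactly at day 2. Averaging over uniform timing in that scenario, the mean hourly-tested time before exposure is 2 × (1 − (12/14)^7) = 1.32 days. This gives 24 × 1.32 + 8 × 0.68 = 37 pairs, or 37/200 = 19%.

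**Sensitivity to the first procedure day** (intravenous insulin for 3, 5 or 7 days, all assumed)
- Day 1: 24/384 = 6% to 24/216 = 11%.
- Day 5: 88/320 = 28% to 120/248 = 48%.

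**Sensitivity to hydroxyurea.** The exclusion starts near day 7 and removes mostly later pairs. Assume one dose a day to month 3 and evenly spread tests, so that 14/24 of later pairs remain:
- low end: 16/(56 + 56 × 14/24 + 160 × 14/24) = 16/182 = 9%;
- high end: 48/(88 + 56 × 14/24 + 56 × 14/24) = 48/153 = 31%.

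**Dilution.** With unexposed share f, the radiation component becomes (1 − f) times its true size: 94% at f = 6%, 76% at f = 24%. As an illustration only, at f = 20% a test with nominal 80% power (two-sided 5%) has power Φ(0.8 × (1.96 + 0.84) − 1.96) = 61%. Restoring it needs 1/0.8² = 1.56 times the sample.

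**Never-exposed participants.** For a Poisson count with mean 6, exp(−6) = 0.25%, or 0.1 of 40. For a negative binomial, (k/(k+6))^k: k = 2 gives 6.3% (2.5 of 40) and k = 1 gives 14.3% (5.7 of 40). The mean of 6 counts all procedures. If only half were performed with the device worn (assumed), exp(−3) = 5.0%, or 2 of 40.

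**The case against.** The strongest reply is that the plan plainly means post-exposure readings. The main goal in Study Procedures and the opening of Analysis and Methods both speak of accuracy after radiation, and the reference to enrolled participants' data may name only the source. This stands as evidence of intent. A reader might infer that the plan instructs analysts to treat unexposed readings as exposed; it does not. But no sentence turns the intent into a selection rule, and the grouping and comparison as written take everything from placement.

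Other stronger readings also fail:

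- **Nearly half the data are unexposed.** Setting 48 early pairs against 56 outpatient pairs suggests this, but it omits the later inpatient pairs.
- **A quarter of participants are never exposed.** A negative binomial with k = 0.5 gives 28%, but it implies a variance of 6 + 36/0.5 = 78. Nothing in the documents supports that.
- **The net result must lean towards no difference.** Only the radiation component is diluted. The comparator is external, and if early postoperative readings are less accurate for other reasons, including them could widen the gap.
- **Pre-exposure pairs are a clean control.** They differ from later pairs in postoperative day, insulin route and hydroxyurea, and outpatient pairs use a different meter. Never-exposed participants are a selected group, because imaging follows complications.

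It is also fair to say that the longitudinal question is less affected. With most procedures in the first two weeks, outpatient pairs are mostly post-exposure, and Statistical Consideration covers both settings.

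**Conclusion.** The point holds as a missing analysis rule. Followed as written, the plan counts pairs before the first uncovered procedure, and any never-exposed participants, as exposed. Any radiation effect is then diluted, chiefly in the inpatient and pooled estimates.

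Under uniform timing of 6 procedures over 14 days with placement at day 0, about 6-24% of all pairs are unexposed, before any hydroxyurea exclusion. The figure depends on how long hourly testing lasts and on whether outpatient checks number 56 or 160. Placement day, length of stay, procedure timing and duration of hourly testing are assumptions, and the share moves substantially with the day of first exposure. Never-exposed participants are probably a minor part. The direction of the net difference from public data cannot be settled from the documents.

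The sponsor should correct this before analysis; it does not call the design into question.

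**What to change.** Add to Statistical Consideration:

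1. The primary exposed set is pairs taken after the first procedure performed with the device worn and uncovered, in participants with at least one such procedure.
2. Inpatient pairs before that procedure are a supportive within-participant baseline, limited to inpatient meter pairs and adjusted for, or interpreted in light of, postoperative day, insulin route and hydroxyurea.
3. Never-exposed participants are reported separately and descriptively.
4. Accuracy is summarised by cumulative number of uncovered procedures.

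This is mostly analysis wording, since procedure dates and apron use are already collected. It is not wholly so: dates alone cannot classify pairs on the procedure day, and absence of an apron does not show whether the device was worn or removed. Record procedure time and whether the device was worn or removed, alongside apron use. Failing that, leave procedure-day pairs out of both sets.

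The cost is somewhat fewer pairs in the exposed set, the small addition to data capture, and a before/after contrast that is not free of confounding and should not be presented as a control arm.
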